An efficacy study of WET as an intervention for motor vehicle accident (MVA)-related PTSD was conducted. In this RCT, participants were randomized to either WET ( $n = 24$ ) or wait-list (WL;  $n = 22$ ). Median time since MVA was 20 months and all of the participants were diagnosed with chronic PTSD using a structured diagnostic interview. Participants that were randomized to WET displayed a large and significant reduction in PTSD symptoms at post-treatment and 3 month follow-up, relative to participants in the WL. WET participants also maintained their treatment gains at the 6 month follow-up assessment. In terms of PTSD diagnosis, at the 3-month follow-up assessment only 4% of the WET participants met diagnostic criteria for PTSD, relative to 67% of the WL participants; 8% of WET participants met PTSD criteria at the 6 month assessment. Although no *in vivo* exposures were included in the WET protocol, the WET participants reported significant reductions in driving and riding avoidance behaviors at the follow-up assessments (15 point reduction for WET compared with 3 point reduction for WL; 12). Not only was WET efficacious in terms of reducing PTSD symptoms, the treatment was also well received and tolerated. Only 2 participants (8%) dropped out of the WET condition. The 8% dropout rate is consistent with the low dropout rates observed in earlier work (6,7,8). This treatment dropout rate compares favorably with the dropout rates reported for PE and CPT, which again are typically around 25-35% (13). The reason for the low dropout rate in WET is unclear but the limited number of sessions in combination with the current study will further extend our investigation of the efficacy of WET by comparing it directly to a first line PTSD treatment, Cognitive Processing Therapy-Cognition only (CPT-C) and testing it in an active duty military sample.

**6. RESEARCH DESIGN.** We will randomize up to 175 active duty military personal who meet diagnostic criteria for PTSD. Participants will be blocked randomized to either WET or CPT-C. Participants will be assessed at baseline (pre-treatment) and 10-, 20-, and 30- weeks following the baseline assessment. Primary outcome measure will be PTSD symptom severity at the assessment time points. PTSD symptom severity will be assessed using the Clinician Administered PTSD Scale for DSM-5 (CAPS-5). Treatment will consist of five weekly sessions for WET condition and twelve twice-weekly sessions for CPT-C.

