**7.1.5. Consent Process.** An authorized and trained member of the research team will engage the potential participant in an interactive explanation of the study guided by the informed consent document (ICD). After the participant has read the ICD, he or she will be given the opportunity to consider participation and discuss the research with family and friends. Once the potential participant has reached a decision, the advising staff member will review the purpose of study, duration of study, study procedures, the experimental components of the study, the potential risks and discomforts, the potential benefits, any alternatives to participation, protection of participant's confidentiality, and the contact information for both the researchers and the regulatory bodies overseeing the conduct of the study with the participant to ensure the participant has an understanding of the study. If the individual is agreeable to participation the advising staff member will then have the individual sign the consent form in the presence of a witness. A copy of the signed ICD will be given to the participant for their reference. Over the conduct of the study, the research team will be available to answer any questions about the research. Ongoing discussions will occur to ensure the participant's questions and concerns are addressed during the conduct of the study. Potential participants will have the study explained to them in a safe and private location before any assessments are conducted within the STRONG STAR offices in San Antonio or STRONG STAR offices in Killeen, TX. The informed consent process will require approximately 20 minutes.

**7.1.6. Subject Screening Procedures.** Once the consent is signed, participants will then be asked to fill out the packet of assessments (see measures section below) with the Independent Evaluator (IE). The initial consent and screening will require 3-4 hours.

**7.1.7. Compensation for participation.** N/A.

**7.1.8. Treatment Procedures.** Participant will be randomized to one of two treatment conditions.

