197 Team will discuss the reasons why and, if needed, coordinate appropriate follow-up outside of this study.
- 198 • Once all the baseline testing is completed, the participant will be randomized to either Written Exposure Treatment  
199 (WET) or Cognitive Processing Therapy – Cognition only (CPT-C) and scheduled to start treatment in accordance  
200 with the condition they were randomized into. Randomization will be stratified to consider gender and PTSD symptom  
201 severity baseline score. Randomization will be done using a table of random numbers.
  - 202 - Written Exposure Treatment (WET). Participants will complete 5, weekly sessions during which they will be  
203 instructed to write about their trauma event for 30 minutes each session. The first session lasts approximately 60  
204 minutes, whereas the remaining four sessions require approximately 40 minutes to complete.
  - 205 - Cognitive Processing Therapy – Cognition only (CPT-C). Participants will complete 12, 60 minute sessions that  
206 will be scheduled twice per week. Treatment focuses on challenging traumatic-related cognitions.
- 207 • Every effort will be made to deliver the therapy in the therapist's office face-to-face. However, in the event that a therapist  
208 is unavailable on-site, a therapist trained in the interventions and located in Texas will provide therapy by video  
209 teleconferencing. Video teleconferencing will be accomplished using the UTHSCSA stand-alone network that allows for  
210 platform-based encryption. The participant will be located in the STRONG STAR offices at Ft Hood using a UTHSCSA  
211 computer and the therapist will be located in their office also using a UTHSCSA computer. Platform-based encryption  
212 technology has been recognized as superior to enterprise networks for data security (Younggren, 2011) and the stand-  
213 alone network allows for full control of scheduling and bandwidth for the research. For this research we will use Cisco  
214 Systems C20 Quickset Telepresence System to create a stand-alone VTC network allowing full control over scheduling  
215 and bandwidth use. The C20 system (also referred to as MOVI or Jabber) meets all of the technical specifications outlined  
216 in the ATA Guidelines, and is easy enough to use that even technical novices should be able to participate successfully in  
217 VTC mental health. Telepresence through the C20 Quickset is encrypted and cloud-based allowing for easy access to any  

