Random effects linear (hierarchical linear) models will be implemented for the primary noninferiority ITT randomized comparison of total CAPS-5 score as well as any secondary analyses. This ITT comparison will disregard all CPT-C non-adherence occurring after randomization under the ITT principal (20). The random effects linear models will consist of a random intercept and slope to account for within-patient correlations for the longitudinal observations across follow-up visits (baseline to 10-, 20-, and 30-weeks assessments). Fixed effects specified separately for each post-baseline visit, the intervention, and their respective interactions will be used to obtain the ITT estimate and one-sided 95% confidence interval for the noninferiority test of change from baseline at the 10 week assessment. The test of noninferiority will be based on showing that this upper bound of the one-sided confidence interval is less than the pre-specified margin of 10 CAPS points that is considered to show that WET is noninferior to CPT-C. The 10 week visit will be used to test noninferiority (**Hypothesis 1**), as this would be the first time point of post-treatment for both treatment conditions. Noninferiority will be claimed if the model-based difference between the two conditions is less than this upper bound. The 30 week post-baseline assessment will be used to examine **Hypothesis 2**.

**Hypothesis 3:** WET will have a significantly lower dropout rate relative to CPT-C.

We will conduct survival and logistic regression models to examine treatment dropout rates between the two conditions. The regression models can incorporate predictors (covariate main effects) of dropout, model the timing of attrition, and explore interactions to supplement the primary test of group differences. We will only classify a participant as a dropout if they did not complete the treatment protocol and dropped out of the treatment for reasons other than feeling better and not needing additional treatment.

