**7.7 Confidentiality.** All in-person therapy sessions and interview assessments will be delivered in private offices in the STRONG STAR offices at the university Northwest Center located at [name] or STRONG STAR offices located at [name] in Killeen, TX. Digital audio recordings of assessments will be labeled with the participant's study id number and saved on a secure password protected server. Those recordings to be reviewed for fidelity to ensure that the treatment is being delivered in accordance with the treatment manual will be viewed on a secure password protected server. There is no option for the reviewers to download or otherwise save the recordings to their computers. Every member of the research team will be trained and monitored about how to handle and protect both medical and research records. Only authorized study staff, and members of the STRONG STAR Data Management and Biostatistics Core staff will have access to either the raw data or electronic study data.

**7.7.1 Certificate of Confidentiality.** We are not seeking a Certificate of Confidentiality

**7.7.2. Data Protection.** Data will be coded using an assigned number. Paper copies of data collected during treatment will be placed into a lock box which will be transported by car to STRONG STAR offices by a STRONG STAR staff member. Data collected during treatment will be placed into locked cabinets at the UTHSCSA STRONG STAR offices at the Northwest Center in San Antonio or the STRONG STAR offices on Fort Hood by a STRONG STAR staff member and then entered into a secure STRONG STAR database. Audio files will be uploaded to a secure STRONG STAR server over an encrypted network connection.. Every member of the research team will be trained and monitored about how to

350 handle and protect both medical and research records. Furthermore, the research team strictly controls access to study  
351 data using policies and procedures developed specifically for the STRONG STAR Research Consortium.  
352 .  
353

354 A Data Safety and Monitoring Plan (DSMP) has been developed in accordance with the National Institutes of Health  
355 Office of Human Research Protection to assure the appropriate clinical safety monitoring of study subjects participating in  
356 this study.  
357

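### Two study locations, but no site term in the primary model or site stratum in the randomisation: a small, cheaply avoided loss of precision

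*Combined protocol and SAP*

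**What the plan says.** **Two locations.** Section 7.1.5 places the consent discussion in the "STRONG STAR offices in San Antonio or STRONG STAR offices in Killeen, TX". Section 7.7 says "All in-person therapy sessions and interview assessments will be delivered in private offices in the" study offices and then names those of the two cities. Section 7.1.4 lists military bases in both areas as recruitment sources.

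**Described differences between them.** Section 7.1.4 gives Fort Hood providers a direct electronic referral route and describes no equivalent for San Antonio. Section 7.3 allows video therapy when no therapist is available on site, and describes the arrangement for one location only: "The participant will be located in the STRONG STAR offices at Ft Hood using a UTHSCSA" computer.

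**Randomisation.** Section 6 says "Participants will be blocked randomized to either WET or CPT-C". Section 7.3 says "Randomization will be stratified to consider gender and PTSD symptom" "severity baseline score. Randomization will be done using a table of random numbers". No section mentions blocking or stratifying by site.

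**Primary model.** Section 7.4.3 says "The random effects linear models will consist of a random intercept and slope to account for within-patient correlations" and "Fixed effects specified separately for each post-baseline visit, the intervention, and their respective interactions will be used" for the noninferiority estimate and limit at 10 weeks. Site appears neither as a fixed nor as a random effect. The same section accepts noninferiority only if it is confirmed in both the modified ITT sample and the per-protocol sample of completers.

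**The concern.** Site is known before randomisation and may be related to outcome. If change in CAPS-5 differs between the two locations and site is in neither the allocation nor the model, two things follow. The between-site variation in change stays in the residual, which widens the one-sided limit compared with 10 points. In any one trial, the arms will also differ somewhat in their share of Killeen participants, and the estimate moves with that difference.

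The per-protocol sample adds a further route. Completion is determined after randomisation, and the arms ask for different commitments: five weekly sessions against twelve twice-weekly sessions with assignments. If completion depends on site differently in the two arms, site can be unbalanced among completers for reasons other than chance, and a larger sample would not remove that. Because the conclusion needs both samples, this route matters as well.

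**Working it through.** **Inputs from the protocol (Section 7.4.1):** margin 10, SD 20, true difference 0, one-sided 0.05, power 0.80, 1:1 allocation, 50 per group required, up to 175 randomised.

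**Assumptions (not in the documents):** share p of participants at one site = 0.5, with 0.8 as an uneven case; site difference in *change* of 5 or 10 points, that is g = 0.25 or 0.50 within-site SDs; within-site SD of the change score = 20.

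**1. The plan's own figure.** n = 2 × (1.645 + 0.842)² × 20² / 10² = 49.5, so 50 per group. The stated figure reproduces.

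**2. Standard error without a site term.** The SD becomes 20 × √(1 + p(1−p)g²).
- g = 0.25: 20 × √1.0156 = 20.16, up 0.8%.
- g = 0.50: 20 × √1.0625 = 20.62, up 3.1%.

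At N=175 the standard error is 20 × √(4/175) = 3.02, and the one-sided half-width is 1.645 × 3.02 = 4.97 points. The increase is 4.97 × 0.0078 = 0.04 points for g = 0.25 and 4.97 × 0.0308 = 0.15 points for g = 0.50.

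**3. Chance shift in the estimate.** The between-arm difference in site share has SD √(4p(1−p)/N). Multiply by 1.96 and by the site difference.

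| N | SD of share difference (p = 0.5) | 95% range of shift, 5 points | 95% range of shift, 10 points |
|---|---|---|---|
| 100 | 0.100 | ±1.0 | ±2.0 |
| 175 | 0.076 | ±0.7 | ±1.5 |

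Equal sites are the worst case, because p(1−p) is largest at 0.5. At 80:20 the ranges are ±0.8 and ±1.6 for N=100, and ±0.6 and ±1.2 for N=175. These are 95% ranges, not maxima.

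**4. Steps 2 and 3 are one effect.** At N=175 and g = 0.50 the shift has SD 10 × 0.0756 = 0.76. Then √(3.02² + 0.76²) = 3.12, which is 3.02 × 1.031. The chance shift is the same extra variance seen from another side and must not be added to it.

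**5. Power (normal approximation, p = 0.5).**

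| N analysed | With site term | Without, g = 0.25 | Without, g = 0.50 |
|---|---|---|---|
| 100 | 0.804 | 0.798 | 0.783 |
| 175 | 0.952 | 0.949 | 0.941 |

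The n needed per group without the term is 51 (g = 0.25) or 53 (g = 0.50), against 50 with it.

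**6. Simulation.** This used 20,000 runs at N=100, with a single change score in place of the full longitudinal model. At a true difference of 10 points, the one-sided type I error was between 0.048 and 0.051 with and without the site term. Power fell from 0.797 to 0.793 (g = 0.25) and from 0.793 to 0.772 (g = 0.50) when the term was left out.

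**7. Per-protocol sample.** The documents give no completion rates by site and arm, so this part cannot be sized. The simulation does not model selection of completers and gives no reassurance about it.

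**The case against.** The strongest reply is that this hardly matters. Chance imbalance is already covered by the confidence limit, and only precision is lost. Under a 5-point site difference that is 0.04 points on the limit at N=175. The tested quantity is change from baseline, so a stable site difference in CAPS-5 *level* largely cancels; only a difference in change counts, and the documents offer no evidence of one. Adding a stratum also has a price. With gender and, say, two severity levels (the protocol does not define them), site would take 4 strata to 8, about 175/8 = 22 people each. Preferring two patient-level stratifiers in a trial of this size is defensible. All of this stands. It limits the size of the point and weakens the case for stratification, but it is no reason to leave a known baseline variable out of the model.

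A reader might infer three stronger things, and the documents support none of them:

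- **That the two locations have separate raters and therapists, so the arm contrast partly compares staff.** The protocol does not say this. Section 7.3 allows a trained therapist located elsewhere in Texas to treat by video, and Section 7.3.2.1 allows assessment by phone or video, so staff need not be tied to a site.
- **That the ITT test is biased or its error rate inflated.** Random allocation makes the site imbalance a matter of chance, and the simulation shows no inflation.
- **That a site term would resolve uneven use of video.** Video follows from a therapist being unavailable, which arises after randomisation and could differ between five and twelve sessions. A site term deals with it only in part.

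**Conclusion.** The omission is real in both places, and its consequence is minor. Under equal sites and an assumed 5 to 10 point site difference in change at SD 20, leaving site out costs 0.8% to 3.1% in standard error. At the 100 analysed participants on which the sample size rests, it costs about two power points at most. Smaller site differences or uneven sites cost less. The percentage loss depends only on the site split and on the site difference in SD units, so it does not rest on 20 being the right SD for the CAPS-5. The type I error of the ITT comparison is not at issue. Possible site imbalance among per-protocol completers is a further reason for the term, of unknown size.

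**What to change.** In Section 7.4.3, add site (San Antonio, Killeen/Fort Hood) and site-by-visit to the fixed effects of the primary model, for both the modified ITT and the per-protocol analyses. The interaction is needed because the test is on change: a site main effect alone would adjust level only. If enrolment has begun, the term can still be prespecified before unblinded data are seen; added afterwards, it would look data-driven if the limit fell near the margin.

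The cost is one sentence and four fixed-effect parameters (site, plus site at each of three post-baseline visits). In the per-protocol analysis the term adjusts for site imbalance, not for other selection into completion.

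Stratifying randomisation by site is optional, because it doubles the number of strata. Whichever is chosen, report the site split by arm in both samples, and the use of video by arm and site as a description, since the site term does not settle that question.

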### 7.4.3 Data analysis.

**Hypothesis 1:** Participants randomly assigned to WET will show noninferior outcomes in PTSD symptom severity at the 10-week assessment relative to participants randomly assigned to CPT-C.

**Hypothesis 2:** Participants randomly assigned to WET will show noninferior outcomes in PTSD symptom severity at the 30-week follow-up assessment relative to participants randomly assigned to CPT-C.

We will conduct analyses on both the modified intent to treat (ITT) sample (requiring only attendance at one treatment session) and on the per-protocol (PP) sample of treatment completers. Several authors (e.g., 16, 19) note that PP analysis is an important supplement to the ITT analysis but not a substitute. Although ITT analyses are widely assumed to have a bias in favor of the null hypothesis of no difference, systematic reviews do not always confirm that. Analyses of the PP sample may also be biased, and in either direction. At this point, we believe the consensus in the field is to perform analyses on both ITT and PP samples, and accept the non-inferiority hypothesis only if it is confirmed in both samples.

Random effects linear (hierarchical linear) models will be implemented for the primary noninferiority ITT randomized comparison of total CAPS-5 score as well as any secondary analyses. This ITT comparison will disregard all CPT-C non-adherence occurring after randomization under the ITT principal (20). The random effects linear models will consist of a random intercept and slope to account for within-patient correlations for the longitudinal observations across follow-up visits (baseline to 10-, 20-, and 30-weeks assessments). Fixed effects specified separately for each post-baseline visit, the intervention, and their respective interactions will be used to obtain the ITT estimate and one-sided 95% confidence interval for the noninferiority test of change from baseline at the 10 week assessment. The test of noninferiority will be based on showing that this upper bound of the one-sided confidence interval is less than the pre-specified margin of 10 CAPS points that is considered to show that WET is noninferior to CPT-C. The 10 week visit will be used to test noninferiority (**Hypothesis 1**), as this would be the first time point of post-treatment for both treatment conditions. Noninferiority will be claimed if the model-based difference between the two conditions is less than this upper bound. The 30 week post-baseline assessment will be used to examine **Hypothesis 2**.

**Hypothesis 3:** WET will have a significantly lower dropout rate relative to CPT-C.

We will conduct survival and logistic regression models to examine treatment dropout rates between the two conditions. The regression models can incorporate predictors (covariate main effects) of dropout, model the timing of attrition, and explore interactions to supplement the primary test of group differences. We will only classify a participant as a dropout if they did not complete the treatment protocol and dropped out of the treatment for reasons other than feeling better and not needing additional treatment.

**7.7 Confidentiality.** All in-person therapy sessions and interview assessments will be delivered in private offices in the STRONG STAR offices at the university Northwest Center located at [name] or STRONG STAR offices located at [name] in Killeen, TX. Digital audio recordings of assessments will be labeled with the participant's study id number and saved on a secure password protected server. Those recordings to be reviewed for fidelity to ensure that the treatment is being delivered in accordance with the treatment manual will be viewed on a secure password protected server. There is no option for the reviewers to download or otherwise save the recordings to their computers. Every member of the research team will be trained and monitored about how to handle and protect both medical and research records. Only authorized study staff, and members of the STRONG STAR Data Management and Biostatistics Core staff will have access to either the raw data or electronic study data.

**7.7.1 Certificate of Confidentiality.** We are not seeking a Certificate of Confidentiality

**7.7.2. Data Protection.** Data will be coded using an assigned number. Paper copies of data collected during treatment will be placed into a lock box which will be transported by car to STRONG STAR offices by a STRONG STAR staff member. Data collected during treatment will be placed into locked cabinets at the UTHSCSA STRONG STAR offices at the Northwest Center in San Antonio or the STRONG STAR offices on Fort Hood by a STRONG STAR staff member and then entered into a secure STRONG STAR database. Audio files will be uploaded to a secure STRONG STAR server over an encrypted network connection.. Every member of the research team will be trained and monitored about how to

350 handle and protect both medical and research records. Furthermore, the research team strictly controls access to study  
351 data using policies and procedures developed specifically for the STRONG STAR Research Consortium.  
352 .  
353

354 A Data Safety and Monitoring Plan (DSMP) has been developed in accordance with the National Institutes of Health  
355 Office of Human Research Protection to assure the appropriate clinical safety monitoring of study subjects participating in  
356 this study.  
357

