### 10 11 12 13 14 15 16 17 18 19 **3. OBJECTIVES/SPECIFIC AIMS/RESEARCH QUESTIONS**

20  
21 **Primary Aim:** To conduct a RCT to examine if WET is noninferior to CPT-C for the treatment of PTSD in active duty military personnel.

- 22 • **Hypothesis 1:** Participants randomly assigned to WET will show noninferior change in PTSD symptom severity at the 10-week assessment relative to participants randomly assigned to CPT-C.
- 23 • **Hypothesis 2:** Participants randomly assigned to WET will show noninferior outcomes in PTSD symptom severity at the 20- and 30-week assessment relative to participants randomly assigned to CPT-C.

24  
25  
26  
27  
28 **Secondary Aim:** Examine whether there are condition differences in treatment dropout rates between WET and CPT-C.

- 29 • **Hypothesis 3:** WET will have a significantly lower dropout rate relative to CPT-C.

30  
31 **4. MILITARY RELEVANCE:** Many military personnel are reluctant to seek treatment from the military treatment facilities and when they do seek out treatment, treatment dropout rates can be high (1). Hoge and colleagues (1) described the current state of treatment utilization and dropout among military personnel as a “call to action to improve treatment engagement and retention” (p. 997). The proposed project addresses this important and much needed area.

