 280 (18). Specifications were a 10 point non-inferiority margin, a standard deviation of 20 (14), a true difference between  
 281 treatment groups of zero, one-sided non-inferiority test at  $p=.05$ , desired power=.80 and equal allocation to the two  
 282 treatment groups. With these specifications, PASS reports that N=50 per group is required (note: the same result is given  
 283 by several free online calculators, e.g., <https://www.sealedenvelope.com/power/continuous-noninferior/>;  
 284 <http://powerandsamplesize.com/Calculators/Compare-2-Means/2-Sample-Non-Inferiority-or-Superiority>). As noted in the  
 285 application, this number was increased twice, first by 25% to account for unavoidable loss to follow-up, and then by an  
 286 additional 20% to deal with the as yet unknown psychometric properties of the CAPS-5. This is the basis for proposed  
 287 recruitment of N=175.  
 288

Estimate Required Sample Size	Up to 175
Estimate Participant Screen Out / Drop Out / Withdrawal	30%
Total Enrollment Requirement	275

289  
 290 **7.4.2 Primary (i.e., primary outcome variables) and secondary endpoints.**  
 291

292 The primary treatment outcome variable in this study is PTSD symptom severity, which is assessed using the CAPS-5. The

CAPS-5 will be administered at baseline, 10-, 20-, and 30- weeks following the baseline assessment. The secondary outcome variable is treatment dropout rate for each treatment condition.

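### The week-10 non-inferiority test compares raw CAPS-5 change with neither stratification factor as a covariate, which gives up precision, and the random slope's time coding is not stated

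*Combined protocol and SAP*

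**What the plan says.** Section 7.3 (Study Procedures) makes baseline severity and gender design factors: "Randomization will be stratified to consider gender and PTSD symptom" severity at baseline.

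Section 7.4.3 then gives the primary model. The fixed part is: "Fixed effects specified separately for each post-baseline visit, the intervention, and their respective interactions will be used to obtain the ITT estimate". The response vector runs from baseline through weeks 10, 20 and 30, and the test is of the week-10 change from baseline. The covariance is described in one sentence: "The random effects linear models will consist of a random intercept and slope to account for within-patient correlations". No time coding, alternative covariance, fallback or sensitivity fit is named. Covariates are mentioned only for the dropout models under Hypothesis 3.

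The change contrast matches Hypothesis 1 in Section 3: "Participants randomly assigned to WET will show noninferior change in PTSD symptom severity at the 10-week assessment". The analysis set is the "modified intent to treat (ITT) sample (requiring only attendance at one treatment session"), alongside a per-protocol (PP) sample, and the plan will "accept the non-inferiority hypothesis only if it is confirmed in both samples".

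Section 7.4.1 sizes the trial on a margin of 10, an SD of 20, a true difference of zero and a one-sided 5% test, with "desired power=.80 and equal allocation to the two" groups. That gives 50 per group; "this number was increased twice, first by 25% to account for unavoidable loss to follow-up", then by 20%, and recruitment is set at 175.

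**The concern.** Because intervention has its own fixed effect, the baseline means are free to differ by arm. The week-10 contrast is then the difference between arms in raw change. Baseline is subtracted with a coefficient of 1; it is not used as a predictor with an estimated coefficient. When the true regression of week 10 on baseline has a slope below 1, subtraction adds noise. The design also balances severity between arms, while the reported standard error takes no account of that balance, so the interval is wider than it needs to be.

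A second, conditional issue is the covariance. A random intercept with a slope linear in time imposes a shape on the variance of change. If most change happens by week 10 and then holds, that shape can understate the variance of the 0-to-10-week change and pull the one-sided limit in, which is the direction that favours a non-inferiority claim.

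At stake are the power of the primary test and how far its limit depends on a covariance assumption that the plan does not check.

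**Working it through.** **Inputs from Section 7.4.1.** Margin 10, SD 20 (used here for follow-up), true difference 0, one-sided 5%, 175 randomized, 25% loss.

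**Assumed, because the documents give no figure.** Correlation ρ between baseline and week 10; baseline SD (SD0); a severity stratum split at the median; correlations between visits.

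**1. The plan's own figure.** n = 2 × (1.645 + 0.842)² × 20² / 10² = 49.5, so 50 per group. At 50, SE = √(2 × 400/50) = 4.00 and power = Φ(10/4 − 1.645) = 80.4%. The stated 50 is reproduced.

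**2. Evaluable number.** 175 × 0.75 / 2 = 65.6; 65 per arm is used.

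**3. Variances per participant.**
- Raw change, as the model reports it: Vc = SD0² + 400 − 40ρ·SD0.
- Raw change, actual sampling variance when a median-split stratum is balanced: Vt = Vc − (2/π)(20ρ − SD0)².
- Baseline-adjusted: Va = 400(1 − ρ²).

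Algebraically Vc − Va = (SD0 − 20ρ)², so the gain disappears when SD0 = 20ρ.

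**4. Power and error, one analysis.** Raw-change power = Φ((10 − 1.645√(2Vc/65)) / √(2Vt/65)). Raw-change error at the margin = Φ(−1.645√(Vc/Vt)). Adjusted power = Φ(10/√(2Va/65) − 1.645).

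Example, SD0 = 20 and ρ = 0.3: Vc = 560, Vt = 435.2, Va = 364. The SEs are 4.15 (reported), 3.66 (actual) and 3.35 (adjusted). Power is 80.7% against 91.0%, and the raw-change error is 3.1%.

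| Baseline SD | ρ | Raw change | Adjusted | Raw-change error |
|---|---|---|---|---|
| 20 | 0.3 | 80.7% | 91.0% | 3.1% |
| 20 | 0.4 | 85.6% | 92.9% | 3.4% |
| 20 | 0.5 | 90.6% | 95.0% | 3.6% |
| 15 | 0.3 | 87.0% | 91.0% | 4.0% |
| 15 | 0.4 | 90.6% | 92.9% | 4.3% |
| 15 | 0.5 | 94.0% | 95.0% | 4.6% |
| 10 | 0.3 | 90.3% | 91.0% | 4.8% |
| 10 | 0.4 | 92.7% | 92.9% | 4.9% |
| 10 | 0.5 | 95.0% | 95.0% | 5.0% |

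**5. Gender.** If gender explains 1% of residual variance, the SE is multiplied by √0.99 = 0.995; if 5%, by √0.95 = 0.975. Nearly all the gain comes from baseline CAPS-5.

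**6. The longitudinal model itself.** Step 4 uses raw change in followed participants, whereas Section 7.4.3 fits all visits. A simulation of that model used 88 per arm, 22 per arm with baseline only, compound symmetry, SD 20, a linear slope and 2,400 runs per case. Single-analysis power at ρ = 0.3, 0.4 and 0.5 was 84, 88 and 91%. Week-10 regression on baseline in the 66 followed per arm gave 92, 92 and 94%. The direction is the same.

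**7. Covariance.** Assumed four-visit covariances were projected by maximum likelihood onto a random intercept plus slope, with complete data and no credit for stratification. Error = Φ(−1.645 × SE ratio).

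| Baseline SD | Correlation with baseline | Between follow-ups | Model SE / true SE, linear slope | One-sided error |
|---|---|---|---|---|
| 20 | 0.47 | 0.75 | 0.81 | 9.0% |
| 20 | 0.50 | 0.70 | 0.86 | 7.8% |
| 15 | 0.50 | 0.70 | 0.91 | 6.7% |
| 20 | 0.50 | 0.50 (compound symmetry) | 1.00 | 5.0% |

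With the slope coded as baseline versus post-baseline, the ratio is 1.00 in every row. Under AR(1) with a linear slope it is 1.03 to 1.11, which is conservative. Once stratification and loss are included, five simulated cases in which change emerges and then holds (linear slope; correlations with baseline 0.40–0.55 and between follow-ups 0.65–0.75; baseline SD 15–20) gave single-analysis error of 6.2–7.0% for the planned model and 4.4–5.6% for the adjusted one. Single-analysis power was about equal (91–97% against 92–96%).

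**The case against.** **Baseline is already used.** A reader might infer that the plan ignores baseline CAPS-5. It does not: baseline is the first response and is subtracted. Hypothesis 1 is about change, so the contrast answers the stated question. What stands is narrower: baseline is not a predictor, and neither stratification factor is a covariate.

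**The trial is not shown to be underpowered.** With PP confirmation also required, the simulation at SD 20 and ρ = 0.3 puts the planned model at 73–79%, depending on the PP numbers assumed, and it is tempting to read this as missing the target. But the .80 in Section 7.4.1 is for one test at 50 per group, and on one analysis the fitted planned model exceeds .80 in every case run. The adjusted model also falls when PP must confirm (to 84–90%), this is the least favourable cell, and loss and PP membership were random in the simulation.

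**An excess of false claims is not shown.** Single-analysis error of 6–7% should not be paired with power under the two-sample rule. Under that rule the planned model's simulated error is 3.5–5.7%, about nominal. Section 7.4.3 also does not say that the slope is linear.

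**The gain may be small.** Entry requires a PTSD diagnosis, so baseline scores may be restricted, and at baseline SD 10 the gain nearly vanishes. SD 20 is a CAPS figure, and Section 7.4.1 itself calls the CAPS-5 properties unknown.

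**The proposed model was not fitted in full.** Week-10 regression with all-or-none random loss and no gender term stood in for it, while Section 7.3.2.1 expects partial follow-up. These points limit the size of the concern. They do not supply the missing covariates or time coding.

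**Conclusion.** The point holds as a loss of precision and a gap in specification. The week-10 test is a raw change comparison that omits both stratification factors. It is not biased. Where baseline spread is close to follow-up spread, it is conservative (one-sided error 3.1–3.6% at baseline SD 20) and gives up about 4 to 10 percentage points of single-analysis power at ρ 0.3–0.5. The loss is 1 to 4 points at baseline SD 15 and under 1 point at SD 10. Gender contributes little.

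The covariance point is conditional. With a slope linear in time and change that emerges by week 10 and then holds, single-analysis error is about 6–7% in the simulation and up to about 9% with complete data and no credit for stratification. With baseline-versus-post coding or equal-SD compound symmetry there is no such excess. It is a second reason for an unstructured covariance, not a demonstrated error. The two effects should not be added: where the reported SE is too small, apparent power is not lost.

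All sizes rest on assumed correlations, baseline SD and stratum split. The change is worth making because it costs little. Confidence in the size is medium.

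**What to change.** For the primary week-10 contrast, model CAPS-5 at weeks 10, 20 and 30 with arm by visit, continuous baseline CAPS-5 by visit, and gender. Use an unstructured covariance across the three visits and name the fallback if it does not converge. Apply the same adjustment to Hypothesis 2 and to PP.

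Baseline as a covariate is the safer default here, because the modified ITT and PP samples are both defined after randomization. As a sensitivity analysis, fit a model with a common baseline mean. Fit it either in all randomized participants or in the modified ITT sample, with the stated assumption that non-attendance at the first session does not differ by arm.

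State the time origin and whether time is nominal visit or actual weeks. The Abstract counts from the start of treatment, Sections 6 and 7.3 count from baseline, and Section 7.3 allows earlier baseline testing to be reused. The effect on the SE ratio is small (at most 0.015 when baseline is placed 2–8 weeks earlier), but any slope model needs the definition.

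If the random intercept and slope stays primary, state its time coding and add the adjusted, unstructured model as a sensitivity analysis.

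**Cost.** SAP wording only. Baseline CAPS-5 and gender are known for everyone randomized. The covariance has 6 parameters against 4. Participants with no follow-up CAPS-5 leave the primary fit; the adjusted simulation figures already bear that cost (66 of 88 per arm used), and the sensitivity analysis keeps them.
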